4.2.3.1.2 Viral Resistance Measurements

Resistance associated variants (RAVs) in the hepatitis C virus can lead to failure of therapy. This is one of the most important considerations when treating with a DAA. To better understand and document the potential for RAVs to impact treatment with MK-3682+MK-8408, blood samples for viral resistance assays are collected at Baseline (Day 1) to determine pre-existing RAVs to MK-3682 and MK-8408. Additional resistance testing on these samples may be performed. Blood samples for resistance testing are also collected during the follow-up period, as well as at the virologic failure confirmation visit (should this occur) for genotypic and investigational assays to assess emergence of resistance to MK-3682 and/or MK-8408 following treatment initiation. RAVs will be assessed for any subject who has detectable virus above 1000 IU/mL and has met a virologic failure criteria.

4.2.3.2 Safety Endpoints

The safety and tolerability of the study regimen will be assessed by a clinical evaluation of AEs and inspection of other study parameters including vital signs, physical examinations, 12-lead electrocardiograms (ECGs), and standard laboratory safety tests at appropriate time points as specified in the Study Flow Chart (Section 6.0). Adverse events are graded and recorded according to Section 7.2. Subjects may be asked to return for unscheduled visits in order to perform additional safety monitoring.

4.2.3.3 Pharmacokinetic Endpoints

The primary pharmacokinetic (PK) endpoint for MK-3682 (and metabolites) and MK-8408 is C_{trough} . PK samples will be collected from all subjects on each visit as described in the Study Flow Chart (Section 6.0) and in Table 12 (Pharmacokinetic Sampling Timepoints). These samples will be used to evaluate not only PK concentrations, but also PK/PD and PK/AE relationships of MK-3682 (and metabolites) and MK-8408, as appropriate. The pre-dose time points outlined were chosen in order to capture C_{trough} for all compounds. The frequency of C_{trough} collections will allow a thorough assessment of both subject drug concentrations and drug compliance, should a breakthrough occur. In addition, the post-dose time points, in conjunction with the other samples, will be used for PK-safety and PK-efficacy modeling.

4.2.3.4 Pharmacodynamic Endpoints

As described in Section 7.1.3.2.2, a subgroup of the study population will be included in an intensive viral kinetic sub-study. The purpose of this sub-study is to determine whether early viral kinetics can aid in developing a PK/PD model that can predict combinations which may be efficacious with various treatment durations.

These subjects will have HCV RNA samples collected during Week 1 as described in the Study Flow Chart (Section 6.0) and in Table 13 (Intensive Viral Kinetic Week 1 Sampling

Timepoints). In addition, PK samples will be collected as described in [Table 12](#) (Pharmacokinetic Sampling Timepoints). These samples will be used to evaluate the PK/PD relationships of MK-3682 (and metabolites) and MK-8408, as appropriate.

4.2.3.5 Planned Exploratory Biomarker Research

Planned Genetic Analysis

Understanding genetic determinants of drug response is an important endeavor during medical research. This research will evaluate whether genetic variation within a clinical trial population correlates with response to the treatment(s) under evaluation. If genetic variation is found to predict efficacy or adverse events, the data might inform optimal use of therapies in the patient population. This research contributes to understanding genetic determinants of efficacy and safety associated with the treatments in this study.

In addition to studying variation across the human genome, for example IL28, genetic variants [46] will specifically be investigated for understanding variation in clinical endpoints for example, but not limited to, SVR and other efficacy safety and measurements.

4.2.3.6 Future Biomedical Research

The Sponsor will conduct Future Biomedical Research on specimens collected for future biomedical research during this clinical trial. This research may include genetic analyses (DNA), gene expression profiling (RNA), proteomics, metabolomics (serum, plasma) and/or the measurement of other analytes.

Such research is for biomarker testing to address emergent questions not described elsewhere in the protocol (as part of the main trial) and will only be conducted on specimens from appropriately consented subjects. The objective of collecting specimens for Future Biomedical Research is to explore and identify biomarkers that inform the scientific understanding of diseases and/or their therapeutic treatments. The overarching goal is to use such information to develop safer, more effective drugs/vaccines, and/or to ensure that subjects receive the correct dose of the correct drug/vaccine at the correct time. The details of this Future Biomedical Research sub-trial are presented in Section 12.2 - Collection and Management of Specimens for Future Biomedical Research. Additional informational material for institutional review boards/ethics committees (IRBs/ERCs) and investigational site staff is provided in Section 12.3.

4.3 Benefit/Risk

Subjects in clinical trials generally cannot expect to receive direct benefit from treatment/vaccination during participation, as clinical trials are designed to provide information about the safety and effectiveness of an investigational medicine.

There remains a critical need for new HCV therapies to address deficiencies in current therapy, including lower than optimal efficacy rates in select patient populations, drug resistance, and a lack of convenience. The two-drug, once-daily combination regimen containing MK-3682 (an HCV NS5B NI) and MK-8408 (an HCV NS5A complex inhibitor) has the potential to simplify treatment paradigms and reduce the need for pretreatment testing by providing a well-tolerated and efficacious regimen for multiple genotypes and diverse patient populations.

MK-3682

MK-3682 is a potent HCV NS5B NI with pangenotypic activity and a high barrier to resistance that, in combination with complementary HCV DAAs, has the potential to benefit an expanded spectrum of HCV-infected subjects, including those with currently difficult-to-treat GTs of HCV and individuals who have failed previous treatments. Among all the known DAA classes, NIs have displayed the broadest HCV genotypic coverage and the highest barrier to the development of resistance.

MK-3682 belongs to a class of uridine-based nucleotide analogs, e.g., SOF, that have been generally well tolerated. However, there have been postmarketing reports of symptomatic bradycardia, including one fatal cardiac arrest and cases requiring pacemaker insertion, in subjects taking the antiarrhythmic drug amiodarone together with either LDV/SOF or SOF in combination with another DAA. The toxicity potential of MK-3682 has been well characterized in *in vitro* mitochondrial toxicity assays, a battery of *in vitro* and *in vivo* genetic toxicity studies, safety pharmacology studies, and 4-week, 3-month and 6-month repeat-dose oral toxicity studies in rats and monkeys. *In vitro* and *in vivo* preclinical data demonstrate that MK-3682 and its metabolite, M6, at the exposures observed in the clinic, have limited potential for class toxicities associated with nucleotides, including myopathy and mitochondrial toxicity. NOAELs in the rat and Cynomolgus monkey at 1000 mg/kg/day provide adequate margins of safety relative to anticipated human doses and support daily oral dosing of humans for up to 6 months in duration. In summary, the toxicity studies identified minimal differences between control and treated animals, all of which were not considered adverse. Preclinical studies identified the liver and potentially kidney as potential target organs. There was no evidence of cardiovascular toxicity in studies up to 3 months duration, based on histopathology in the rat and monkey and echocardiography, electrocardiography, and serum biomarker evaluations in the monkey. Overall, the preclinical toxicity profile of MK-3682 via the oral route of administration supports the continuation of clinical trials.

To date, MK-3682 has been generally well tolerated in healthy subjects and HCV-infected subjects in several Phase 1 clinical studies at single doses up to 900 mg, multiple doses up to 750 mg per day for 10 days, and in Phase 2a trials of 300 mg or 450mg once daily for up to 24 weeks. Review of the safety data has revealed no clinically significant abnormalities in routine physical examinations including vital signs. There have been no dose-related or other patterns observed in the clinical, ECG or laboratory data. In the clinical studies proposed, available safety data (clinical and laboratory AEs, vital signs, laboratory safety tests, and ECGs) will be carefully monitored.

Phase 2 studies have demonstrated that a regimen of MK-3682 (450mg)/GZR/MK-8408 is highly effective in GT1, 2, and 3-infected subjects. Overall, MK-3682, as a component of a combination DAA regimen, has the potential to substantially improve HCV treatment outcomes, benefiting many HCV-infected individuals.

MK-8408

MK 8408 is a potent HCV NS5A complex inhibitor with pangenotypic activity that has the potential to benefit individuals requiring treatment of HCV infection, even if the individual is infected with currently difficult-to-treat GTs. The improved potency of MK-8408 against RAVs observed with earlier generation NS5A inhibitors suggests that MK-8408 will have

improved efficacy in individuals who have experienced treatment failures with other anti-HCV regimens and/or have NS5A RAVs at baseline.

MK-8408 has favorable safety findings in safety assessment toxicity studies and ancillary pharmacology studies, supporting the continued evaluation of MK-8408 in clinical trials in adults. The 2-week, 3-month, 6-month, and 9-month rat and dog toxicity studies provide substantial preclinical safety margins for doses proposed to be administered in future clinical trials. MK-8408 has been given to approximately 217 subjects and subjects in 8 MK-8408 Phase 1 trials and in over 800 subjects in ongoing Phase 2a trials (MK-8408 in combination with MK-3682 and GZR in HCV GT1, 2, and 3-infected subjects). MK-8408 has been administered at doses up to 600 mg/day (10 times the proposed clinical dose), 100 mg given daily for 10 days, and 60mg once daily for up to 24 weeks. No serious adverse experiences have been reported in any individual receiving MK-8408. There were no consistent treatment-related changes in labs, vital signs, or ECG safety parameter values. Adverse experiences in subjects receiving MK-8408 monotherapy have been mild to moderate in intensity and transient in duration. The totality of the safety data indicates that MK-8408 is well-tolerated.

Definitive embryo-fetal developmental toxicity studies conducted in concordance with the International Conference on Harmonisation of Technical Requirements for Registration of Pharmaceuticals for Human Use (ICH) M3 (R2) guidance have been completed in rats and rabbits for MK-3682 and MK-8408. Data support the inclusion of women of childbearing potential in clinical trials with MK-3682 and MK-8408. Inclusion of women of childbearing potential should be in accordance with the study protocol and applicable regulatory guidance.

Based on the preclinical data and the clinical experience to date in healthy subjects and HCV-infected subjects, the risk/benefit assessment is favorable for proceeding with the proposed clinical study with the two-drug combination of MK-3682+MK-8408.

Additional details regarding specific benefits and risks for subjects participating in this clinical trial may be found in the accompanying Investigators Brochure (IB) and Informed Consent documents.

5.0 METHODOLOGY

5.1 Entry Criteria

5.1.1 Diagnosis/Condition for Entry into the Trial

Male/Female subjects of at least 18 years of age with chronic HCV infection will be enrolled in this trial.

5.1.2 Subject Inclusion Criteria

In order to be eligible for participation in this trial, the subject must:

1. be ≥ 18 years of age on day of signing informed consent.
2. have HCV RNA ($\geq 10,000$ IU/mL in peripheral blood) at the time of screening.
3. have documented chronic HCV GT1, GT2, GT3, GT4, GT5, or GT6 (with no evidence of non-typeable or mixed genotype) infection and meet the definition below:

- Positive for anti-HCV antibody, HCV RNA, or HCV GT1, GT2, GT3, GT4, GT5, or GT6 at least 6 months before Day 1
- OR
- Positive for anti-HCV antibody or HCV RNA with a liver biopsy consistent with chronic HCV infection (such as the presence of fibrosis) before Day 1
4. be otherwise healthy as determined by the medical history, physical examination, ECG, and clinical laboratory measurements performed at the time of screening.
 5. have liver disease staging assessment as follows:

Absence of cirrhosis is defined as any one of the following:

- Liver biopsy performed within 24 months of Day 1 of this study showing absence of cirrhosis
- Fibroscan performed within 12 months of Day 1 of this study with a result of ≤ 12.5 kPa
- A Fibrosure[®] (Fibrotest[®]) score of ≤ 0.48 **and** aspartate aminotransferase (AST) to Platelet Ratio Index (APRI) of ≤ 1 during Screening

Compensated cirrhosis is defined as any one of the following:

- A liver biopsy performed prior to Day 1 of this study showing cirrhosis (F4)
- Fibroscan performed within 12 calendar months of Day 1 of this study with a result > 12.5 kPa
- A FibroSure[®] (Fibrotest[®]) performed during Screening with a score of > 0.75 **and** an aspartate aminotransferase (AST): platelet ratio index (APRI) of > 2 . APRI formula: $AST \div \text{lab ULN for AST} \times 100 \div (\text{platelet count} \div 100)$ (APRI calculation to be provided by the central laboratory)

NOTE: In the absence of a definitive diagnosis of presence or absence of cirrhosis by the above criteria, a liver biopsy or Fibroscan is required. Liver biopsy results supersede the results obtained by Fibroscan[®] or Fibrosure[®]

6. be HCV treatment-naïve (defined as no prior exposure to any IFN, RBV, or other approved or experimental HCV-specific direct-acting antiviral agent) OR be HCV treatment-experienced (defined as prior virologic failure after treatment with an IFN-containing regimen, with or without ribavirin, or intolerance to an IFN-containing regimen). Subjects may not have previously received treatment with HCV direct-acting antiviral agents
7. meet one of the following criteria:
 - a) The subject is a male who is not of reproductive potential, defined as a male who has azoospermia (whether due to having had a vasectomy or due to an underlying medical condition).
 - b) The subject is a female who is not of reproductive potential, defined as a female who either: (1) is postmenopausal (defined as at least 12 months with no menses in

women ≥ 45 years of age); (2) has had a hysterectomy and/or bilateral oophorectomy, bilateral salpingectomy, or bilateral tubal ligation/occlusion at least 6 weeks prior to screening; OR (3) has a congenital or acquired condition that prevents childbearing.

c) The subject is a female or a male who is of reproductive potential and agrees to avoid becoming pregnant or impregnating a partner beginning at least 2 weeks prior to administration of the initial dose of study drug through 14 days after taking the last dose of study drug (or longer if dictated by local regulations) by complying with one of the following: (1) practice abstinence[†] from heterosexual activity OR (2) use (or have their partner use) acceptable contraception during heterosexual activity. Acceptable methods of contraception are[‡]:

Single method (one of the following is acceptable):

- intrauterine device (IUD)
- vasectomy of a female subject's male partner
- contraceptive rod implanted into the skin

Combination method (requires use of two of the following):

- diaphragm with spermicide (cannot be used in conjunction with cervical cap/spermicide)
- cervical cap with spermicide (nulliparous women only)
- contraceptive sponge (nulliparous women only)
- male condom or female condom (cannot be used together)
- hormonal contraceptive: oral contraceptive pill (estrogen/progestin pill or progestin-only pill), contraceptive skin patch, vaginal contraceptive ring, or subcutaneous contraceptive injection

[†]Abstinence (relative to heterosexual activity) can be used as the sole method of contraception if it is consistently employed as the subject's preferred and usual lifestyle and if considered acceptable by local regulatory agencies and ERCs/IRBs. Periodic abstinence (e.g., calendar, ovulation, sympto-thermal, post-ovulation methods, etc.) and withdrawal are not acceptable methods of contraception.

[‡]If a contraceptive method listed above is restricted by local regulations/guidelines, then it does not qualify as an acceptable method of contraception for subjects participating at sites in this country/region.

8. understand the study procedures, alternative treatments available, risks involved with the study, and voluntarily agrees to participate by giving written informed consent.
9. provide written informed consent for the trial. The subject may also provide consent for Future Biomedical Research. However, the subject may participate in the main trial without participating in Future Biomedical Research.

For HIV co-infected subjects these additional criteria must also be met:

10. have HIV-1 infection documented by any licensed rapid HIV test or HIV enzyme or chemiluminescence immunoassay (E/CIA) test kit at any time prior to study entry

(Day 1) and confirmed by a licensed Western blot or a second antibody test by a method other than the initial rapid HIV and/or E/CIA, or by HIV-1 p24 antigen, or plasma HIV-1 RNA VL.

11. meet one of the following criteria:

- a. not currently be on antiretroviral therapy (ART) and have no plans to initiate ART treatment while participating in this study.
 - i. subjects not on ART must have CD4+ T-cell count >500 cells/mm³ at time of screening
- b. have well controlled HIV on ART, defined as:
 - i. subjects on ART must have a CD4+ T-cell count >200 cells/mm³ at time of screening
 - ii. subjects on ART must have achieved and maintained virologic suppression (defined as confirmed HIV RNA level below the LLOQ of available assay at the time of screening) for at least 8 weeks prior to screening
 - iii. subjects on ART must have been on a stable regimen, without changes in drugs or dose modification, for at least 4 weeks prior to study entry (Day 1)
 - iv. the combination ART regimen must not contain any antiretroviral medications other than: tenofovir, abacavir, lamivudine, emtricitabine, raltegravir, dolutegravir or rilpivirine

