NOTE: If any of the laboratory exclusion criteria below in [Table 8](#) are met, the site may have the abnormal value retested one time.

Table 8 Laboratory Exclusion Criteria

Laboratory Assessment	Exclusionary Values
Creatinine Clearance (estimated glomerular filtration rate, eGFR) ¹	<50 mL/min/1.73 m ²
Hemoglobin	<10 g/dL
Platelets	<50 × 10 ³ /μL
Total Bilirubin	>2.0 mg/dL unless history of Gilbert's disease (If Gilbert’s disease is the proposed etiology, this must be documented in the subject’s chart)
Serum Albumin	<3.0 g/dL
INR	>1.7 unless subject has a stable INR on an anticoagulant regimen
ALT	>10× ULN
AST	>10× ULN
¹ Creatinine clearance will be evaluated as an estimated GFR (eGFR) based on the modification of diet in renal disease (MDRD) equation: $\text{eGFR (mL/min/1.73 m}^2\text{)} = 175 \times (\text{Scr, std})^{-1.154} \times (\text{Age})^{-0.203} \times (0.742 \text{ if female}) \times (1.212 \text{ if black})$ Scr, std: serum creatinine measured with a standardized assay	

14. Is or has an immediate family member (e.g., spouse, parent/legal guardian, sibling or child) who is investigational site or sponsor staff directly involved with this trial.

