7.1.2.7 Non-Invasive Methods of Cirrhosis Evaluation

FibroScan[®] - This method for assessing liver cirrhosis has gained increasing acceptance. In the US, this methodology is FDA approved and in other countries it is often the preferred method of assessment. FibroScan[®] results are influenced by a number of confounders including ALT, ascites, and underlying disease. Hepatitis C is one of the best studied and is the disease state with the most reproducible/reliable results. Fibroscan has been evaluated in many liver diseases for the staging of liver fibrosis, and has been demonstrated to be very effective for differentiating cirrhosis (F4) from no cirrhosis (<F4), but it is less capable of differentiating gradations of fibrosis. In a large study by Castera et al. [47] in a population of subjects with chronic hepatitis C, a cut-off of 12.5 kPa was selected for cirrhotics. At this cut-off, the sensitivity and specificity of the test for cirrhosis were 87% and 91%, respectively, and the negative predictive value was 95%. Since this analysis was assessed specifically in subjects with chronic hepatitis C, the cut-off value ≤ 12.5 kPa used by Castera was selected to exclude cirrhotics in the current study.

FibroTest[®] + APRI: – Various methodologies have been developed in order to improve the sensitivity and specificity of blood tests used to diagnose cirrhosis in subjects with chronic hepatitis C infections. One such algorithm, the Sequential Algorithm for Fibrosis Evaluation (SAFE), which uses a combination of Fibrotest and the aspartate aminotransferase-to-platelet ratio index (APRI), is very accurate for diagnosing cirrhosis [48]. For cirrhosis, the SAFE for F4 algorithm provides a diagnostic accuracy of 89.5% with a negative predictive value of 94.6%. Using this algorithm, it is estimated that only 6.2% of the subjects would need a liver biopsy to confirm the diagnosis of cirrhosis. The cut-off values for excluding cirrhotics using the two tests, without the use of liver biopsy, are ≤ 1 and ≤ 0.48 for FibroTest[®] and APRI when the SAFE for F4 is used. This study uses this method with one variation and that is the more stringent requirement that both the APRI and FibroTest[®] need to be consistent with no cirrhosis, i.e. APRI is ≤ 1 AND FibroTest[®] ≤ 0.48 . Accordingly, the Sponsor is confident these cut-off values will differentiate cirrhotic from non-cirrhotic subjects with reasonable accuracy in this study.

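### The APRI formula printed in inclusion criterion 5 has no platelet unit and does not fit its own cut-offs of 1 and 2 in either usual unit

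*Combined protocol and SAP*

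**What the plan says.** Criterion 5 in Section 5.1.2 offers three routes to each status. For absence of cirrhosis, the blood-test route needs a FibroTest score of 0.48 or less together with an "aspartate aminotransferase (AST) to Platelet Ratio Index (APRI) of" 1 or less. For compensated cirrhosis it needs FibroTest above 0.75 together with an "aspartate aminotransferase (AST): platelet ratio index (APRI) of" more than 2. The formula follows: AST divided by its ULN, times 100, divided by (platelet count ÷ 100). No platelet unit is given, and the entry ends with "APRI calculation to be provided by the central laboratory".

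The NOTE under criterion 5 requires a biopsy or Fibroscan when these criteria give no definitive status. It also lets biopsy override the other methods.

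Table 8 (Section 5.1.3) lists the "laboratory exclusion criteria". It excludes platelets below 50 × 10^3/µL and AST above 10 × ULN, and for an abnormal result "the site may have the abnormal value retested one time".

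Section 7.1.2.7 explains the choice of cut-offs: "This study uses this method with one variation and that is the more stringent requirement that both the APRI" and FibroTest agree that cirrhosis is absent. The preceding sentence, which begins "The cut-off values for excluding cirrhotics using the two tests, without the use of liver biopsy", lists the two values in reversed order, giving 1 to FibroTest and 0.48 to APRI.

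**The concern.** Dividing the platelet count by 100 after multiplying by 100 puts the score on a scale that does not match cut-offs of 1 and 2. If one cut-off cannot be reached and the other is met by almost everyone, APRI no longer acts as the second test that Section 7.1.2.7 relies on, and FibroTest alone decides one of the two labels.

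Cirrhosis status determines three things:
- **Safety exclusions.** The Child-Pugh and hepatocellular carcinoma exclusions (Section 5.1.3, criteria 3 and 7) and the liver imaging requirement (Section 6.0, footnote 2) apply only to cirrhotic subjects. A false non-cirrhotic label would bypass them.
- **Enrollment targets.** Table 1 aims for about 15 cirrhotic subjects in each of Arms 1 to 4 (in Arm 1, about 10 GT1a plus 5 GT1b). Arms 5 and 6 have no target.
- **Subgroup results.** Section 8.10 estimates SVR12 and SVR24 by cirrhosis status. With about 15 cirrhotic subjects per arm, a few wrong labels would matter.

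**Working it through.** The plan gives no worked APRI value to reproduce, so the check evaluates the printed formula at the plan's own limits.

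**Inputs**
- Formula and cut-offs: criterion 5.
- AST at most 10 × ULN and platelets at least 50 × 10^3/µL (50,000 per µL): Table 8. The plan sets no lower limit for AST and no upper limit for platelets.

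**Simplification.** Let R = AST ÷ ULN and P = platelet count. Then APRI = R × 100 ÷ (P ÷ 100) = 10,000 × R ÷ P.

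**Case A: P in 10^3/µL, the unit of Table 8**
- R = 1, P = 200: 10,000 × 1 ÷ 200 = 50.
- APRI ≤1 requires R ≤ P ÷ 10,000, which is 0.005 at P = 50, 0.02 at P = 200 and 0.045 at P = 450. If the AST ULN is 40 IU/L (an assumption; range 30 to 50), the last of these is an AST of 1.8 IU/L (1.35 to 2.25).
- APRI >2 requires R > 2P ÷ 10,000, which is only 0.03 at P = 150.
- On a grid of R from 0.05 to 10 and P from 50 to 450, no combination gives APRI ≤1.

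The no-cirrhosis cut-off is therefore out of reach in practice, and nearly everyone passes the cirrhosis cut-off.

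**Case B: P per µL**
- The largest score within the Table 8 limits is 10,000 × 10 ÷ 50,000 = 2.0, which does not exceed 2. On the same grid, no combination gives APRI >2.
- APRI ≤1 holds for R up to 50,000 ÷ 10,000 = 5 at the platelet floor, and up to the AST ceiling of 10 once P is at least 100,000.

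**Other reading of the division order.** Taking AST ÷ (ULN × 100) ÷ (P ÷ 100) gives R ÷ P. The maximum is 10 ÷ 50 = 0.2 in case A and 10 ÷ 50,000 = 0.0002 in case B, so >2 is again unreachable.

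**A scale on which both cut-offs work.** With R × 100 ÷ P and P in 10^3/µL:
- R = 1, P = 200 gives 0.5.
- R = 4, P = 100 gives 4.0.
- R = 10, P = 50 gives 20.

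The printed score is 100 times this value in case A and one tenth of it in case B.

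**Who could be wrongly labelled**
- Case A: FibroTest 0.80, R = 1, P = 250. The printed score is 40, so the label is cirrhotic. The rescaled score is 0.4, so the two tests disagree and the NOTE requires a biopsy or Fibroscan.
- Case B: FibroTest 0.40, R = 5, P = 100,000. The printed score is 0.5, so the label is non-cirrhotic. The rescaled score is 100 × 5 ÷ 100 = 5, again indeterminate.

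**The case against.** A reader might infer that cirrhosis status is misassigned, and for every subject staged by FibroTest with APRI. The documents do not support that, for three reasons.

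- **An unreachable cut-off assigns no label.** The NOTE under criterion 5 sends subjects without a definitive status to biopsy or Fibroscan. The unreachable side of the formula therefore costs extra procedures. A wrong label can come only from the cut-off that has become too easy.
- **FibroTest must still qualify.** Where FibroTest and a properly scaled APRI agree, the subject keeps the right label or goes to the fallback.
- **The central laboratory supplies APRI.** Nothing shows that it programmed the printed expression.

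All three stand and limit the scope, but the NOTE does not catch the two examples above, because those subjects receive a definitive label.

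The printed divisor may also reflect a digit lost when the formula was converted to text. A divisor of 1000 with platelets per µL would make both cut-offs reachable, and this cannot be excluded. It would not make the missing unit harmless: in the Table 8 unit, R = 1 and P = 200 would then score 1 × 100 ÷ (200 ÷ 1000) = 500.

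The effect on the trial is also limited. All subjects are assigned the same 12-week regimen by genotype. Cirrhosis is not a stratification factor (Section 5.4) and does not enter the SVR12 estimate by arm (Section 8.6.1). It is one of eleven descriptive subgroup factors. Decompensated disease and the Table 8 limits exclude subjects whatever their staging. This is correct and bears on weight, but criterion 5 is an operative rule and two safety exclusions depend on it.

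The reversed values in Section 7.1.2.7 are a slip in describing the cited algorithm. The next sentence states the study's rule in line with criterion 5, and no one is staged by the reversed wording.

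**Conclusion.** The inconsistency is real. As printed, the formula fits its cut-offs in neither usual platelet unit. Per µL, the failure follows from the Table 8 limits (maximum 2.0 against a requirement of more than 2). The only exception is a score built from an out-of-range first value that later passed on retest. In 10^3/µL it is a practical rather than a strict impossibility, because the plan sets no AST floor or platelet ceiling.

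Misassignment is possible, not shown. It requires that the laboratory used the printed formula and that the subject was staged by FibroTest with APRI. It also requires a properly scaled APRI that does not support the label: 2 or less with FibroTest >0.75 (case A), or above 1 with FibroTest ≤0.48 (case B). The documents do not give the share of subjects staged this way, so the effect on the cirrhotic targets and subgroup estimates cannot be sized. The primary analysis by arm is unaffected.

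The form with no further divisor is inferred from both cut-offs becoming reachable; the documents do not state it.

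**What to change.** 1. In criterion 5, state the platelet unit and correct the divisor so that formula and cut-offs agree. One form that does so is (AST ÷ ULN) × 100 ÷ platelets in 10^3/µL, which equals × 100 ÷ (platelets per µL ÷ 1000). The sponsor should confirm the intended form against the source PDF.
2. Ask the central laboratory which formula and unit it programmed.
3. If it used the printed formula, recompute APRI and cirrhosis status from stored AST and platelet values before the subgroup analyses, and list the subjects whose label becomes indeterminate.
4. As a minor wording correction, put the two cut-offs in Section 7.1.2.7 in the order that matches criterion 5.

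The cost is a text correction and one laboratory query. AST and platelets are already collected, so any recomputation needs no new samples.
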